### 5.5.2. Progression of dosing from sentinel subject to the rest of the dosing group (Part A)

The study design allows for sentinel dosing prior to dose administration to the rest of the cohorts, in part A of the study. Guidance is given below for progression of dosing following dosing of the sentinel subjects, in Part A.

Sentinel subjects in Part A should be under constant supervision after dosing. If dose limiting toxicity develop at any other time than described in the guidance below, the Investigator should contact the sponsor at the earliest convenience on the day when the observation is made.

**Table 8 Guidance for progression criteria for sentinel subjects to the rest of dosing group A**

Day of Dosing:	Action:	Observation:	Result:
On Day 1 of the dosing of the sentinel subject, at 6 hours post-dose (immediately prior to the skin prick)	The Investigator will review the available safety data from this subject.	If NO dose limiting toxicity is observed, the skin prick test may be conducted at the Investigator's discretion, according to protocol, and dosing may proceed for the rest of the dosing group.  The Investigator is required to document this decision and to inform the sponsor in writing at the earliest convenience. This time should not exceed 24 hours post dose .	If dose limiting toxicity is observed, the PI or designee should immediately contact the medical monitor or designee (on the day they observe issues). GSK will then decide whether it is necessary for the SMC to be convened immediately or not, and will advise on dose progression or not.
On Day 2 of the dosing of the sentinel subject, and at 6 hours post-dose of Day 1* of the rest of the subjects.	The Investigator reviews the available data of sentinel subject's Day 1 and Day 2  AND available data of 3 subjects at least from the rest of the subjects' Day 1 up to that point.	If NO dose limiting toxicity is observed, the skin prick test may be conducted at the Investigator's discretion, according to protocol, in the rest of the subjects.  Dosing may proceed with Day 3 of the sentinel subject, and Day 2 of the rest of the dosing group.	If dose limiting toxicity is observed, the Investigator or designee should immediately contact the medical monitor or designee (on the day they observe issues). GSK will then decide whether it is necessary for the SMC to be convened immediately or not, and will advise on

Day of Dosing:	Action:	Observation:	Result:
		The Investigator is required to document this decision and to inform the sponsor in writing at the earliest convenience.	dose progression or not.
On Day 3 of the dosing of the sentinel subject, and at 6 hours post-dose of Day 2* of the rest of the subjects.	The Investigator reviews the available data of sentinel subject's Day 2 and Day 3  AND available data of 3 subjects at least from the rest of the subjects' Day 2 up to that point.	If NO dose limiting toxicity is observed, the skin prick test may be conducted at the Investigator's discretion, according to protocol, in the rest of the subjects.  Dosing may proceed with Day 3 of the rest of the dosing group.  The Investigator is required to document this decision and to inform the sponsor in writing at the earliest convenience.	If dose limiting toxicity is observed, the Investigator or designee should immediately contact the medical monitor or designee (on the day they observe issues). GSK will then decide whether it is necessary for the SMC to be convened immediately or not, and will advise on dose progression or not.

\* Assuming the sentinel subject is dosed 1 day before the rest of the subjects.

### **5.5.3. Progression from dosing group 1 to dosing group 2 in Part A, and from Part A to Parts B and C**

#### **5.5.3.1. Progression from dosing group 1 to dosing group 2 in Part A**

At the end of dosing group 1 in Part A, the decision to proceed to the next higher strength and dose for dosing group 2 will be made by the SMC based on a safety report from the PI or designee, on the clinical safety, tolerability, up to and including the follow up visit, and pharmacokinetic exposure up to 24 hours after the last dose, in at least 6 subjects at the highest dose level.

These dose adjustments may involve either an increase or a decrease in the planned dose in terms of strength of cream used (0.5% or 1%) and/or extent of body surface area and the decision on whether to dose once or twice daily in Parts B and C.

#### **5.5.3.2. Progression from Part A to Parts B and C**

At the end of Part A, the decision to proceed to the dosing of patients in Parts B and C will be made by the SMC based on a safety report from the PI or designee on the clinical safety, tolerability, pharmacokinetic exposure and effect on systemic biomarker (CD69 expression), of all subjects in Part A. A decision will also be made whether the data support progressing with females of child-bearing potential in Parts B and C of the study.

A decision may be made for the dose to take forward to Parts B and C only if data are available from dosing group 1 and dosing group 2 of Part A for at least 6 completed subjects in Group 2. All the other data available for subjects who may not have completed the study should also be presented in the safety report from the PI or designee.

The actual doses to be administered may be adjusted based on safety, tolerability and preliminary pharmacokinetic data at previous dose levels; these dose adjustments may involve either an increase or a decrease in the planned dose.

The dosing schedule may also be adjusted to expand a dosing cohort to further evaluate safety, pharmacokinetic findings at a given dose level, or to add cohorts to evaluate up to 1% strength and up to 20% BSA. The study procedures for these additional subject(s) or cohort(s) will be the same as that described for other study subjects.

#### **5.5.3.3. Progression in Part B and from Part B to Part C**

In Parts B, the first 4 subjects will be randomised so that one of the 4 subjects will receive placebo and the three other subjects will receive GSK2646264. An interim review of the preliminary data from the first 4 subjects, after they have completed the study, will be conducted before dosing the rest of the patients in Part B (n=12 total). Preliminary PK, safety, and tolerability data up to and including the follow-up visit, will be reviewed by the SMC (See Section 5.5). In addition, further modeling of PK parameters after 3 days of dosing in these first 4 cold urticaria patients focusing on the elimination of the compound, will be performed to aid the decision to move forward to the rest of the subjects in Part B and to Part C, taking into account the pre-determined safety margins (See Appendix 6).

#### **5.5.3.4. Progression within Part C**

Dosing in Part C will only commence once relevant data from the first four subjects in Part B have been reviewed, (see Section 5.5.3.3) to allow greater confidence in predictions of the pharmacokinetics in Part C. The BSA over which study treatment will be administered in Part C is anticipated to be 10%, but is subject to change if appropriate based on preliminary data from Part B. However, the maximum BSA will not exceed 20%.

The first four subjects of Part C will be randomised so that one of the four subjects will receive placebo and the three other subjects will receive GSK2646264. An informal review of the preliminary data from the first 4 subjects may be conducted after they have completed the study. PK, safety and tolerability data up to and including the follow-up visit, will be reviewed by the Sponsor. If required, a discussion with the SMC regarding any changes or adjustments to the dosing regimen in Part C will be held. Recruitment of the full planned cohort (n=16) may continue during any data review. The dosing regimen or study population may be adjusted as appropriate after this interim review for the rest of the subjects in Part C..

## **5.6. Safety Related Study Specific Dose Adjustment Criteria**

If AEs which are of severe intensity and are similar across subjects in the group, or if unacceptable pharmacological effects, reasonably attributable in the opinion of the investigator to dosing with GSK2646264, or if dose limiting toxicity (see Section 5.5.1), are observed in 2 or more subjects in dosing group 1 or dosing group 2 of part A, the dose escalation will be stopped. Relevant reporting and discussion with the GSK medical monitor and the SMC will take place. A substantial amendment will be submitted to the Ethics committees and Regulatory authorities for approval prior to any resumption of dosing.

If AEs which are of severe intensity and are similar across subjects in either Part B or C, or if unacceptable pharmacological effects, reasonably attributable in the opinion of the investigator to dosing with GSK2646264, or if dose limiting toxicity (see Section 5.5.1), are observed in 2 or more subjects in either Part B or C, relevant reporting and discussion with the GSK medical monitor and the SMC will take place.

If a Serious Adverse Event (SAE) occurs in 1 subject and is deemed to be drug related, the dose escalation in Part A, or the study if in Part B or Part C, will be stopped. Relevant reporting and discussion with the GSK medical monitor and the SMC will take place. A substantial amendment will be submitted to the Ethics committees and Regulatory authorities for approval prior to any resumption of dosing.

The above criteria will apply regardless of whether pharmacokinetics are less than the above mentioned PK stopping criteria and every effort will be made to take a blood sample at the time of the event for pharmacokinetics analysis in the presence of any of the above events.

## **5.7. Stopping Criteria for a subject**

### **5.7.1. Liver Chemistry Stopping Criteria**

Liver chemistry threshold stopping criteria have been designed to assure subject safety and to evaluate liver event aetiology (in alignment with the FDA premarketing clinical liver safety guidance).

Study treatment will be stopped **for a subject** if the following liver chemistry stopping criteria is met:

- ALT  $\geq$  3xULN

NOTE: Refer to [Appendix 1](#) for details of the required assessments if a subject meets the above criteria.

### **5.7.2. QTcF Withdrawal Criteria**

A subject that meets either criterion below will be withdrawn from the study. The same QT correction formula (e.g QTcF) should be used to determine inclusion and discontinuation for any individual subject throughout the study.

- QTcF > 500 msec,
- Change from baseline: QTcF >60 msec

If a subject in Part B or Part C has underlying bundle branch block the following withdrawal criteria should be used instead:

Baseline QTcF value (with underlying bundle branch)	QTcF withdrawal criteria
<450 msec	>500 msec
450-480 msec	≥530 msec

Withdrawal of subjects is to be based on an average QTcF value of triplicate ECGs. If an ECG demonstrates a prolonged QT interval, then obtain 2 more ECGs over a brief period of time and then use the averaged QTcF values of the 3 ECGs to determine whether the subject should be discontinued from the study

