### **3.2.1.3. Part C: Chronic Spontaneous Urticaria Subjects**

This part of the study will provide safety, tolerability, PK and PD from dosing every 3 days, over a total period of 7 days (with an additional 2 weeks follow-up post last dose for PK, safety and biomarker endpoints) to enable further clinical studies in this population.

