### **3.2.2.3. Additional preliminary data from Part B**

A population pharmacokinetic model integrating all plasma data from part A and the preliminary data from n=4 in part B lead to an estimation of the half life of 57 hours for GSK2646264. This model shows that in order to maintain a 1.8 fold margin with the  $AUC$  NOAEL to allow women of child bearing potential in the trial the doses of 180mg (10% BSA) should be administered every three days, over a total 7 day duration, rather than every day.

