### 5.7.3. Safety related Stopping criteria for an individual subject

A subject may be withdrawn from the study if they present dose limiting toxicity (as defined in Section 5.5.1; also refer to tolerability assessment definition in Section 6.3.4.1.). If dose limiting toxicity is observed in an individual, the Investigator or designee may use their medical judgment and stop dosing the individual subject, and is required to immediately inform the GSK medical monitor or designee. They will then decide whether it is necessary for the SMC to be convened immediately or not, for review of the data and decision on dose adjustment or withdrawal of the individual subject.

A subject may be withdrawn from the study if they present a Serious Adverse Event (SAE), regardless of its severity, and reasonably attributable in the opinion of the investigator to dosing with GSK2646264.

A subject will be withdrawn if they require concomitant medications listed in Section 5.15.

Dosing to an individual may be stopped due to unacceptable local tolerability as evidenced by dose limiting toxicity (as defined in Section 5.5.1).

Tolerability assessments on treated skin areas will be made using the criteria in Section 6.3.4.1.

In the presence of any of the above events, every effort will be made to take a blood sample at the time of the event for pharmacokinetics analysis.

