### 7.1.3. Definition of Adverse Events

An AE is any untoward medical occurrence in a patient or clinical investigation subject, temporally associated with the use of a medicinal product, whether or not considered related to the medicinal product.

NOTE: An AE can therefore be any unfavorable and unintended sign (including an abnormal laboratory finding), symptom, or disease (new or exacerbated) temporally associated with the use of a medicinal product.

Events meeting the definition of an AE **include**:

- Any abnormal laboratory test results (hematology, clinical chemistry, or urinalysis) or other safety assessments (e.g., ECGs, radiological scans, vital signs measurements), including those that worsen from baseline, and felt to be clinically significant in the medical and scientific judgement of the investigator.
- Exacerbation of a chronic or intermittent pre-existing condition including either an increase in frequency and/or intensity of the condition.
- New conditions detected or diagnosed after study treatment administration even though it may have been present prior to the start of the study.
- Signs, symptoms, or the clinical sequelae of a suspected interaction.
- Signs, symptoms, or the clinical sequelae of a suspected overdose of either study treatment or a concomitant medication (overdose per se will not be reported as an AE/SAE unless this is an intentional overdose taken with possible suicidal/self-harming intent. This should be reported regardless of sequelae.).
- When skin tolerability is assessed, a “dermal scoring” of 2 or above, and a score of C, F, G or H in “other effects scoring (ii)”, will be reported as adverse event.

Events that **do not** meet the definition of an AE include:

- The disease/disorder being studied, or expected progression, signs, or symptoms of the disease/disorder being studied, unless more severe than expected for the subject's condition.
- Medical or surgical procedure (e.g., endoscopy, appendectomy); the condition that leads to the procedure is an AE.
- Situations where an untoward medical occurrence did not occur (social and/or convenience admission to a hospital).
- Anticipated day-to-day fluctuations of pre-existing disease(s) or condition(s) present or detected at the start of the study that do not worsen.

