## 12. APPENDICES

### 12.1. Appendix 1: Liver Safety Process

The procedures listed below are to be followed if a subject meets the liver chemistry stopping criteria defined in Section 5.7.1:

- Immediately withdraw the subject from study treatment
- Notify the GSK medical monitor within 24 hours of learning of the abnormality to confirm the subject's study treatment cessation and follow-up.
- Complete the "Safety Follow-Up Procedures" listed below.
- Complete the liver event case report forms. If the event also meets the criteria of an SAE (see Section 7.1.4), the SAE data collection tool will be completed separately with the relevant details.
- Upon completion of the safety follow-up withdraw the subject from the study unless further safety follow up is required
- Do not restart investigational product
- Refer to the Flow chart for a visual presentation of the procedures listed below.

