#### **In addition, for all subjects with $ALT \geq 3 \times ULN$ , every attempt must be made to also obtain the following:**

- Viral hepatitis serology including:

---

[figure not shown]
 INR testing not required per protocol and the threshold value does not apply to subjects receiving anticoagulants.

- Hepatitis A IgM antibody.
- Hepatitis B surface antigen and Hepatitis B Core Antibody (IgM).
- Hepatitis C RNA.
- Cytomegalovirus IgM antibody.
- Epstein-Barr viral capsid antigen IgM antibody (or if unavailable, obtain heterophile antibody or monospot testing).
- Hepatitis E IgM antibody.
- Blood sample for pharmacokinetic (PK) analysis, obtained within 24 hours of last dose. Record the date/time of the PK blood sample draw and the date/time of the last dose of study treatment prior to blood sample draw on the CRF. If the date or time of the last dose is unclear, provide the subject's best approximation. If the date/time of the last dose cannot be approximated OR a PK sample cannot be collected in the time period indicated above, **do not obtain a PK sample**. Instructions for sample handling and shipping are included in the SPM.
- Serum creatine phosphokinase (CPK) and lactate dehydrogenase (LDH).
- Fractionate bilirubin, if total bilirubin  $\geq$  2xULN.
- Assess eosinophilia
- Record the appearance or worsening of clinical symptoms of hepatitis (fatigue, nausea, vomiting, right upper quadrant pain or tenderness, fever, rash or eosinophilia) on the AE CRF.
- Record use of concomitant medications, acetaminophen, herbal remedies, other over the counter medications, or putative hepatotoxins on the Concomitant Medications CRF.
- Record alcohol use on the Liver Events CRF.

The following are required for subjects with ALT  $\geq$  3xULN **and** bilirubin  $\geq$  2xULN ( $>35\%$  direct) but are optional for other abnormal liver chemistries:

- Anti-nuclear antibody, anti-smooth muscle antibody, and Type 1 anti-liver kidney microsomal antibodies.
- Serum acetaminophen adduct HPLC assay (quantifies potential acetaminophen contribution to liver injury in subjects with definite or likely acetaminophen use in the preceding
- Liver imaging (ultrasound, magnetic resonance, or computerized tomography) to evaluate liver disease.
- The Liver Imaging and/or Liver Biopsy CRFs are also to be completed if these tests are performed.

Refer to the diagram below for a visual presentation of the procedures listed above.

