## Follow-up of AEs and SAEs

After the initial AE/SAE report, the investigator is required to proactively follow each subject at subsequent visits/contacts. All AEs and SAEs will be followed until resolution, until the condition stabilizes, until the event is otherwise explained, or until the subject is lost to follow-up.

The investigator is obligated to perform or arrange for the conduct of supplemental measurements and/or evaluations as may be indicated or as requested by GSK to elucidate as fully as possible the nature and/or causality of the AE or SAE. The investigator is obligated to assist. This may include additional laboratory tests or investigations, histopathological examinations or consultation with other health care professionals. If a subject dies during participation in the study or during a recognized follow-up period, the investigator will provide GSK with a copy of any post-mortem findings, including histopathology.

New or updated information will be recorded in the originally completed data collection tool. The investigator will submit any updated SAE data to GSK within the designated reporting time frames.

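### The QTcF rule in Section 5.7.2 takes the subject out of the study rather than off treatment, and nothing then requires the remaining planned PK, thyroid and safety assessments in Parts B and C

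*Protocol*

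**What the plan says.** Section 5.7.2 sets QTcF limits (above 500 msec, or a rise from baseline of more than 60 msec, with separate limits for bundle branch block) and states: "A subject that meets either criterion below will be withdrawn from the study". The decision uses the mean of a triplicate ECG. Nothing after that confirmation is prescribed. Section 4.5 and the Time and Events tables contain no early-withdrawal visit.

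The liver rule works differently. Section 5.7.1 stops study treatment, and Appendix 1 then prescribes follow-up, including "Blood sample for pharmacokinetic (PK) analysis, obtained within 24 hours of last dose". Study withdrawal comes last: "Upon completion of the safety follow-up withdraw the subject from the study unless further safety follow up is required".

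Section 5.7.3, on other individual stopping events, adds that "every effort will be made to take a blood sample at the time of the event for pharmacokinetics analysis".

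Sections 3.2.1.2 and 3.2.1.3 plan Parts B and C "with an additional 2 weeks follow-up post last dose for PK, safety and biomarker endpoints". Section 3.2.2.3 reports that a population model of Part A and early Part B data "lead to an estimation of the half life of 57 hours for GSK2646264". Section 2.1 lists the 12-lead ECG among the primary safety endpoints.

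**The concern.** A stopping rule should end exposure and keep observation. As written, this one ends study participation. The subject with a confirmed QTcF prolongation in a first-in-human study is the one whose later concentrations, thyroid function and ECG recovery are of most interest, and the protocol does not oblige anyone to collect them. The post-dose period exists because the drug is eliminated slowly. The ECGs most likely to trigger the rule come at the end of dosing, so withdrawal would protect little through dose avoidance while putting the follow-up data at risk.

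**Working it through.** The plan gives no figure on this point to reproduce. The check compares the rules, counts doses and samples from protocol Sections 6.1.1 to 6.1.4, and applies the stated half-life.

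**1. What each rule requires after the trigger**

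- Liver (5.7.1, Appendix 1): stop treatment, prescribed follow-up with a PK sample, then study withdrawal.
- Other individual events (5.7.3): possible withdrawal, with a PK sample at the event.
- QTcF (5.7.2): study withdrawal after the confirmatory triplicate; nothing further stated.

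**2. Doses spared at the first scheduled ECG after Day 1**

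| Part | First ECG after Day 1 | Last dose | Doses spared |
|---|---|---|---|
| A, group 1 | Day 4 | Day 3 | 0 |
| A, group 2 | Day 8 | Day 4 | 0 |
| B | Day 3 | Day 3 | 0 or 1 of 3 |
| C | Day 7 | Day 7 | 0 or 1 of 3 |

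In Parts B and C the ECG has no stated time relative to the dose, hence the range. Part C also has a Day 1 ECG: a trigger there would spare 3 of 3 doses if pre-dose and 2 of 3 if post-dose. An unscheduled ECG could also spare more.

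**3. Assessments that would no longer be required**

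Part B PK samples: 3 days × 5, plus Day 4, plus Days 6, 9, 12 and 15, plus follow-up = 15 + 1 + 4 + 1 = 21. After Day 3 there are 6 (6/21 = 29%). If withdrawal precedes the Day 3 dose, the four later samples that day go too, making 10 of 21. Also forgone are 3 thyroid panels (Day 4, Days 10–12, follow-up), the later CD69 samples, 2 serum pregnancy tests where applicable, and the follow-up ECG and laboratory tests.

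Part C PK samples: 3 days × 2, plus Days 10, 15 and 22 = 6 + 3 = 9. After Day 7 there are 3 (3/9 = 33%), or 4 of 9 if withdrawal precedes the Day 7 dose. Also forgone are 3 thyroid panels, 3 CD69 samples, 2 serum pregnancy tests where applicable, the Day 8 DLQI, and the Day 22 ECG and laboratory tests.

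Part A: essentially the one follow-up visit.

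**4. Drug remaining at those visits**

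Residual fraction = 0.5^(h/57), with h the hours since the last dose.

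| Part B (dose Day 3) | h | Residual | Part C (dose Day 7) | h | Residual |
|---|---|---|---|---|---|
| Day 4 | 24 | 75% | Day 10 ± 1 | 48–96 | 56–31% |
| Day 6 ± 1 | 48–96 | 56–31% | Day 15 ± 1 | 168–216 | 13–7% |
| Day 9 ± 1 | 120–168 | 23–13% | Day 22 ± 1 | 336–384 | 1.7–0.9% |
| Day 12 ± 1 | 192–240 | 10–5% | | | |
| Day 15 ± 1 | 264–312 | 4–2% | | | |
| Days 17–19 | 336–384 | 1.7–0.9% | | | |

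If the last dose was given, sampling stops at most 12 h after it in Part B (12/57 = 0.21 half-lives) or 4 h in Part C (4/57 = 0.07). If withdrawal precedes that dose, the last sample is the pre-dose one, about 24 h (0.42 half-lives) or 72 h (1.26) after the previous dose. None of these spans is long enough for an individual half-life estimate.

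The only later scheduled ECG in Parts B and C falls where about 1–2% remains. Keeping the planned visits would therefore not by itself show QTcF recovery; ECGs at the intermediate visits are needed as well.

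**5. Share of the active group**

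At 3:1, Part B has 12 × 3/4 = 9 active subjects and Part C has 16 × 3/4 = 12. One active subject is 1/9 = 11% or 1/12 = 8%.

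**The case against.** A reader might infer that the rule cancels all follow-up. The documents do not support that.

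- Appendix 2 requires adverse events to be followed to resolution or stabilisation, and obliges the investigator to arrange "supplemental measurements and/or evaluations as may be indicated or as requested by GSK". An ECG change is an adverse event if it is "felt to be clinically significant in the medical and scientific judgement of the investigator", and a triplicate-confirmed QTcF above these limits would probably be judged so.
- Sections 6, 6.3 and 6.4.3.1 let safety and PK time points be added without an amendment.
- Section 7.2.2 withdraws a pregnant subject from the study yet still follows her, so withdrawal here does not always mean loss of contact.
- Section 4.5 places QTcF among dose adaptation and stopping criteria, so treatment-only stopping may have been meant.
- The PK sentence in 5.7.3 refers to the events above it and closes Section 5.7; it may or may not reach back to 5.7.2.
- The Study Procedures Manual, which is not available here, may say more.

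All of this stands, and it narrows the point. These provisions permit or partly require follow-up of the event. None requires the remaining scheduled PK, thyroid, CD69 or pregnancy samples after a QTcF withdrawal. If treatment-only stopping was intended, 5.7.2 says something else and needs the same edit.

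A reader might also infer that such a subject would not be replaced, from SAP Section 11.5.1. That SAP was written to Amendment 2, before Parts B and C became parallel-group, and protocol Section 4.1 aims for about 12 subjects completing Part B. Replacement under the current design is not settled. In any case it would restore the headcount, not this subject's exposure and QTcF data.

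The PK loss should not be overstated either. Half-life is a secondary endpoint, reported only if the data allow, and a truncated profile can still contribute to a population model.

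**Conclusion.** The point holds as a gap in a required action: 5.7.2 ends study participation, and no other text makes the remaining scheduled assessments mandatory. For a trigger at the Part B Day 3 or Part C Day 7 ECG, the rule spares at most one of three doses and can forgo roughly 30% or more of the planned PK samples (at least 6 of 21, or 3 of 9) and three thyroid panels. In Part A it matters little.

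The loss follows from the wording together with the absence of a withdrawal visit; the protocol does not say in words that visits stop. The residual percentages assume single-exponential decline from the last dose at the estimated 57 h half-life, with no continued absorption from the cream. The size is per affected subject.

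A reader might infer a suspected QT hazard from the existence of the rule. The documents report none and give no event frequency, and entry generally requires QTcF of 450 msec or less (480 with bundle branch block). This is a worthwhile low-cost improvement, not a flaw that threatens the study.

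**What to change.** Reword 5.7.2 so that, when the criterion is met:

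- study treatment is permanently discontinued;
- the subject continues the scheduled safety and PK assessments to the follow-up visit, unless consent is withdrawn;
- a PK sample is taken at the event;
- ECGs are repeated at the existing visits until QTcF returns towards baseline (Part B Days 4, 6, 9, 12 and 15; Part C Days 10 and 15), in addition to the scheduled follow-up ECG.

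The number of doses spared does not change, so protection from further exposure is the same. The cost is a wording change plus, per affected subject, one PK sample and at most 5 extra ECGs in Part B or 2 in Part C, with no new visits after the event. Some subjects may decline to continue.
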